## 6.4 Exclusion Criteria

For the main objective, patients are not eligible if they have a diagnosis of any of the following conditions in the 180 days before the cohort entry date:

- Epilepsy;
- Bulimia;
- Anorexia nervosa;
- Surgical procedure for weight loss.

Patients also must not have been prescribed opioids or monoamine oxidase inhibitors in the 180 days before entry into the cohort.

Patients with prescriptions for both NB and lorcaserin will be randomly assigned to a baseline treatment group to preserve sample size and mitigate selection bias.

Patients are not eligible for inclusion in the comparability study if they have any of the following, as feasibly measured in the Arcadia data, including:

- Congestive cardiac failure;
- Known left ventricular ejection fraction <20%;
- Moderate or higher pulmonary hypertension ;
- Known severe valvular disease;
- Moderate renal impairment, severe renal impairment, or end-stage renal disease;
- Severe hepatic impairment;
- Use of other products intended for weight loss;
- Use of, within 1 month prior to baseline, more than one other serotonergic drug including, but not limited to:
  - Selective serotonin reuptake inhibitors;
  - Serotonin norepinephrine reuptake inhibitors;
  - Tricyclic antidepressants;
  - Bupropion;
  - Triptans;
  - St. John's Wort and tryptophan;
  - Monoamine oxidase inhibitors, linezolid, dextromethorphan, lithium;
  - Tramadol, antipsychotics or other dopamine antagonists;
- Use of drugs known to increase the risk for cardiac valvulopathy within 6 months prior to baseline including, but not limited to:
  - Cyproheptadine;
  - Amoxapine;
  - TCAs;
  - Mirtazapine;
  - Pergolide;
  - Ergotamine;

- Methysergide;
- Cabergoline;
- History or evidence of clinically significant disease (e.g., malignancy, cardiac, respiratory, gastrointestinal, renal or psychiatric disease);
- Use of lorcaserin HCl within 6 months prior to screening;
- Hypersensitivity to lorcaserin HCl or any of the excipients.

The full list of exclusion criteria are included in the CAMELLIA-TIMI 61 publication and protocol.

[figure not shown]
Similar to the exclusion criteria for the primary objective, patients with any of the diagnoses or prescriptions for opioids and/or monoamine oxidase inhibitors in the 180 days prior to the index event date will be excluded from the case-crossover analysis.

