	
Inclusion and exclusion criteria for the main objective will ensure that only new users are included, and that the NB and comparison groups are comparable on risk factors for MACE after application of propensity score (PS) matching weights.
 
Inclusion and exclusion criteria for the additional objectives will align with those used in the 2018 trial assessing cardiovascular endpoints among lorcaserin users, insofar as the data support a comparable replication.
		
Variables:	
The key variables are initiation of NB, initiation of lorcaserin (active comparator), time on treatment, and the endpoint of MACE. The individual components of MACE will also be quantified. Covariates will be derived from clinical measurements, past medical history, diagnoses, observations, and prescription records. Multiple imputation will be applied to address missing data, coupled with PS analyses to address confounding.
		
Data Sources:	
EHR and linked claims data from Arcadia Data Research. The data currently cover approximately 75 million people in the U.S.
		
Study Size:	
There are approximately 37,000 apparent NB initiators in the Arcadia data.
 
There are approximately 16,000 apparent lorcaserin initiators.
		
Data Analysis:	
Descriptive statistics of the study cohorts, multiple imputation of missing covariates, estimation of crude incidence rates of MACE among initiators of NB, and adjusted incidence rates of MACE after applying PS matching weights will be calculated (1.0 and 1.1). Analogs to intention-to-treat and per-protocol cohort analyses will be conducted. The analysis will also follow the principles of the RCT DUPLICATE Initiative (2.0 and 2.1) to assess the concordance between findings in an EHR study to those in the lorcaserin cardiovascular safety endpoints trial. In addition, we will conduct a case-crossover study to assess the effects of NB on MACE (2.2) and other sensitivity analyses.
		
Milestones:	
 
 Start of Data Collection End of Data Collection	September 2014 February 2020	
 
	Start of Data Collection End of Data Collection	September 2014 February 2020
Start of Data Collection End of Data Collection	September 2014 February 2020		

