**Figure 1. NB safety study design**

[figure not shown]

For the cohort, among the subset of patients with EHR data whose records can be linked to health insurance claims, we will assess the concordance between receiving a prescription for NB and lorcaserin (in the EHR) and filling the prescription (in the claims).

The time of entry into the NB cohort will be the date of first prescription for those taking CONTRAVE®, the date of the second overlapping prescription of naltrexone or bupropion in the case of concomitant use of naltrexone and bupropion, or the date of first prescription for lorcaserin from date of approval in the U.S. to withdrawal from the market, as applicable.

In the case-crossover study, a 90-day hazard window will immediately precede the index event date within which the occurrence of a prescription or dispensing will define exposure status. Similarly, a 90-day referent window will precede the hazard window, with exposure status designated comparably. A 30-day washout window between the hazard and referent windows will be used to mitigate any carryover effects from the prior exposure. Please see **Figure 2** for a visual depiction of the case-crossover study design.

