Follow-up time will be calculated separately for each study endpoint. Patients will be followed starting the day after initial exposure until the first of the following censoring events: (1) the study endpoint of interest, (2) death (for those who do not have the endpoint of interest), or (3) end of available data for those who do not have the event of interest (i.e., censoring due to end of available EHR data). Person-time will be calculated by summing the days from cohort entry (day 0) to the date of the first relevant censoring event.

To test the robustness of assumptions about the date of censoring, analyses with differing censoring definitions will be performed, and estimates compared:

- To assess whether the censoring date needs to be adjusted, the physician consultant will review a random sample of patient health profiles to determine whether there is a clear indicator of censoring. Insofar as there appears to be a clear indicator of censoring, the physician will record this date (blinded to exposure), and this information will be used to

adjust the censoring date. Indeed, this information may be treated as an annotation for a machine learning model.

- To account for a patient still being on the insurance plan but not accessing the healthcare system, adjust the end of follow-up to be 6 months, 1 and 2 years following their last healthcare encounter in the EHR.
- To assess the reliability of our method for computing time until censoring in the EHR, compare follow-up times in the EHR to those observed in the claims enrollment files using a subset of those with EHR and claims data.
- To test robustness of the method for computing follow-up time in the EHR, compute the distribution of follow-up times based on enrollment spans within the subset of individuals with claims and EHR data and apply the median follow-up time within populations with particular health profiles.
- To implement a more specific definition of follow-up time, assume that a last healthcare encounter with a primary care provider, endocrinologist, or geriatric care provider in combination with no death information is the end of enrollment.

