### 9.5.1 Intention-to-Treat Analysis

The ITT defines each day of follow-up for everyone according to their exposure status at the time of cohort entry (e.g., initiation of NB). Classification of person-time in the ITT analysis is subject to exposure misclassification as individuals discontinue treatment or switch to the other study drug before their end of follow-up. In contrast, the ITT estimate preserves the balance in

baseline covariates that will be achieved through PS matching weights because individuals remain in the cohort to which they were assigned at baseline, when the PS weights are applied. The results from this approach are best interpreted as providing an estimate of the effect of starting treatment – or intending to start treatment – on the rate of the outcomes.

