### 9.5.2 As-Treated Analysis

The ITT analysis will be juxtaposed with analyses of person-time classified by actual exposure to NB and lorcaserin, grouped into categories of current, recent, and past use. These person-time classifications estimate the effect of being on (or off) the treatment on the rate of the outcomes. Such estimates are often desirable for drug safety questions because they avoid misclassification of exposure that arises in ITT analysis; however, the balance introduced at baseline by PS matching weights may deteriorate as patients switch non-randomly among different study drugs. Therefore, the ITT and *as-treated* analyses are best interpreted together.

To obtain the hazard ratios necessary to compare trial results to those obtained through use of RWD, we will use an ITT analysis for the primary analyses, and as-treated for sensitivity analyses, as was done in the CAMELLIA-TIMI 61 trial.

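### Patients prescribed both drugs are randomly assigned an arm with no visible limit to starts at baseline and no use of prescription order, so a later prescription can decide the ITT arm

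*Combined protocol and SAP*

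**What the plan says.** Section 6.4 deals with patients who have both drugs in one sentence: "Patients with prescriptions for both NB and lorcaserin will be randomly assigned to a baseline treatment group". The stated reasons are to keep patients in the sample and to limit selection bias. No time window or order of prescriptions is mentioned.

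Section 6.5.1 gives each drug its own entry date. For NB it is the first CONTRAVE prescription, or the second of the overlapping component prescriptions. For lorcaserin it is "the date of first prescription for lorcaserin from date of approval in the U.S. to withdrawal from the market". The section does not say which date applies to a patient with both. Section 6.5.2 adds: "Patients will be followed starting the day after initial exposure".

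Section 6.3 requires 180 days before entry without either drug. This looks back only and places no limit on prescriptions after entry.

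Section 9.5.1 is explicit about the primary contrast: "The ITT defines each day of follow-up for everyone according to their exposure status at the time of cohort entry". It expects that "individuals discontinue treatment or switch to the other study drug before their end of follow-up", and it keeps such patients in their baseline group. Section 9.5.2 warns that "the balance introduced at baseline by PS matching weights may deteriorate as patients switch non-randomly among different study drugs".

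**The concern.** Random allocation is reasonable for a patient who is compatible with both arms at time zero, such as one who starts both drugs on the same day. A patient who starts one drug and later receives the other is compatible with only one arm at first entry. The rule as written draws an arm for that patient too, and the draw is triggered by a later prescription. There are two ways to apply it.

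- **Entry at the assigned drug's first prescription** (the more natural reading of section 6.5.1). If the second drug is drawn, the patient's event-free time on the first drug leaves that arm. Patients who had MACE and therefore never switched stay in it.
- **Entry at first exposure** (suggested by section 6.5.2). Some patients then carry the label of a drug they have not yet started, contrary to section 9.5.1.

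Both use information from after first entry. Propensity-score weights balance baseline covariates and cannot undo this. At stake is the primary result, the NB-versus-lorcaserin IRR for MACE.

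**Working it through.** **The plan's own figure.** Section 8.2 claims more than 80% power for a relative risk of 2.0. Mean follow-up is not in the text and Figure 3 is not visible, so this cannot be reproduced exactly. With 37,000 versus 16,000 patients and 2 per 1,000 person-years (PY), a two-sided 5% Wald test on the log rate ratio passes 80% once mean follow-up reaches about 0.62 years. The figure is not contradicted, and the point here does not depend on it.

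**Inputs from the plan.** About 37,000 NB initiators (sections 3 and 8.1); "There are approximately 16,000 apparent lorcaserin initiators" (section 3); r = 0.002 MACE per PY (section 8.2).

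**Assumptions, because the plan gives no switching data.** True IRR 1.00; D dual users = 5-20% of 16,000 = 800-3,200, counted in both totals; 50:50 draw, so h = D/2 = 400-1,600 are given their second drug; switch at T = 1 year; total follow-up F = 2-4 years; MACE prevents a later switch.

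**Formulas.**

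- All lorcaserin first, entry at assigned drug: IRR = (16,000 − h)F / [16,000F − h(F − 1)]. For entry at first drug, multiply by [(37,000 − D)F + h(F − 1)] / [(37,000 − D)F + hF].
- All NB first, entry at assigned drug: IRR = [37,000F − h(F − 1)] / [(37,000 − h)F]. For entry at first drug, multiply by [(16,000 − D)F + hF] / [(16,000 − D)F + h(F − 1)].

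**Largest case, D = 3,200, F = 2** (events/PY):

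| Order | Entry | NB | Lorcaserin | IRR |
|---|---|---|---|---|
| Lorcaserin first | assigned drug | 138.4/69,200 | 60.8/28,800 | 0.947 |
| Lorcaserin first | first drug | 138.4/70,800 | 60.8/28,800 | 0.926 |
| NB first | assigned drug | 144.8/70,800 | 54.4/27,200 | 1.023 |
| NB first | first drug | 144.8/70,800 | 54.4/28,800 | 1.083 |

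**Smallest case, D = 800, F = 4:** 0.994 and 0.991 (lorcaserin first, assigned-drug and first-drug entry); 1.003 and 1.009 (NB first).

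**Milder conditions, over D = 800-3,200.** Half in each order: 0.998-0.983 (assigned-drug entry) and 1.000 (first-drug entry). If only 30% of MACE prevents a switch: 0.998-0.984 and 0.997-0.977 (lorcaserin first); 1.001-1.007 and 1.003-1.024 (NB first). Assigning by first drug gives 1.000 in every case.

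**Scale.** Unweighted SE of log IRR at 2 years = √(1/148 + 1/64) = 0.150, a 95% CI of 0.75-1.34 around 1. At 4 years it is √(1/296 + 1/128) = 0.106, or 0.81-1.23. The largest shifts are |ln 0.947|/0.150 = 0.36 SE (assigned-drug entry) and ln 1.083/0.150 = 0.53 SE (first-drug entry).

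**Matching weights.** Simulating the largest lorcaserin-first case with matching weights, on one covariate shifted 0.7 SD between arms, gave 0.948 and 0.925. The weights left the shift in place.

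**Washout.** Suppose all 1,600 patients given NB as their second drug fail the 180-day washout and are dropped. The NB arm becomes 33,800 × 2 = 67,600 PY with 135.2 events, a rate of 0.002, and the IRR is still 0.947. The shift comes from the event-free time removed from the lorcaserin arm.

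**Heavier switching, outside the 5-20% range.** A simulation assumed 10% a year switching from lorcaserin and 1% a year from NB, so that about 26% of lorcaserin-first patients had switched by 3 years and 39% by 5 years. It gave 0.93-0.94 at 3 years and 0.90-0.91 at 5 years. Assigned-drug entry with a 180-day washout gave 0.94 and 0.91. Less unequal rates (5%/2% or 10%/4%) gave 0.96-0.98 with assigned-drug entry and 1.00-1.02 with first-drug entry. Simulation error is about 1%.

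**The case against.** The strongest reply is that the sentence was meant only for patients who hold both drugs at baseline. It sits among criteria assessed at or before entry, it speaks of a baseline group, and section 9.5.1 handles later switching separately. On that reading the problem disappears. Nothing visible states it, however. A figure in section 6.4 and Figure 1 are not shown and might narrow the rule, so the point holds for the visible text only.

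A second reply is that the washout bars direct switchers from entering on their second drug. If eligibility is tested before the draw, fewer patients are affected, and that part stands. It does not remove the problem for those with two eligible dates. If eligibility is tested after the draw, the shift remains, as shown above.

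A third is that the sizes rest on assumptions and the SE yardstick is generous. This stands. The larger shifts need every MACE to prevent a switch and one order to dominate. With about 16,000 effective patients per arm (assumed, to mimic matching weights), the 2-year SE is √(1/64 + 1/64) = 0.177, and the largest shifts fall to about 0.31 and 0.45 SE.

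Fourth, the as-treated analysis in section 9.5.2 classifies time by actual exposure. If entry is at first exposure it does not use the random label, so it helps. If entry is at the assigned drug, it does not restore the first-drug time already lost. The case-crossover analysis uses no arm assignment and is unaffected, but it is a sensitivity analysis.

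A reader might infer that the rule makes NB look safer than it is, or that the primary comparison is unsound. The documents support neither. Lorcaserin users are identified from 2012 and NB users from September 2014 (section 6.1), which makes lorcaserin-first sequences plausible but does not show that they dominate. NB-first sequences push the IRR the other way.

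**Conclusion.** The point holds, conditional on the visible text. The rule lets a non-random prescription after first entry set the ITT arm, contrary to section 9.5.1. It leaves the entry date of dual users undefined, and for sequential users it does not deliver the reduction in selection bias given as its reason. The bias is probably small and of unknown sign. With dual use at an assumed 5-20% of lorcaserin initiators, the IRR at a true value of 1.00 lies between about 0.93 and 1.08 at the extremes, at most about half an SE. It lies within 0.98-1.02 if order is balanced or if only 30% of MACE prevents a switch. More frequent and strongly one-sided switching could move it further, but the plan contains nothing to show that this occurs. This is an inexpensive improvement and no threat to the study's validity.

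**What to change.** Replace the sentence in section 6.4 with:

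> A patient prescribed both drugs is assigned to the first of the two for which all eligibility criteria, including the 180-day washout, are met, enters on that date, and stays in that arm for the ITT analysis. Random allocation is used only when both drugs are first prescribed on the same day. The number of patients with both drugs, and their order, will be reported.

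Leave as-treated classification to the existing current, recent and past use scheme in section 9.5.2. If the sentence was always meant for patients with both drugs at baseline, the new text records most of that intent and settles the entry date.

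The cost is a few sentences and a simple change to the cohort program. Prescription dates are already needed for the as-treated analysis, and nearly all dual users are kept. There are two downsides. A few dual users who are eligible at neither date are lost. Also, more dual users with lorcaserin starts before September 2014 stay in the lorcaserin arm, at dates with no contemporaneous NB initiators. The reported counts and order would show how many.

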## 6.5 Variables

### 6.5.1 Exposure

Initiation of NB and lorcaserin will be identified using Hierarchical Ingredient Code Lists (HICLs) from First Databank. If necessary, individual searches of National Drug Codes (NDCs) and free-text strings will also be used. See **Figure 1** for visual depiction of the study design.

**Figure 1. NB safety study design**

[figure not shown]

For the cohort, among the subset of patients with EHR data whose records can be linked to health insurance claims, we will assess the concordance between receiving a prescription for NB and lorcaserin (in the EHR) and filling the prescription (in the claims).

The time of entry into the NB cohort will be the date of first prescription for those taking CONTRAVE®, the date of the second overlapping prescription of naltrexone or bupropion in the case of concomitant use of naltrexone and bupropion, or the date of first prescription for lorcaserin from date of approval in the U.S. to withdrawal from the market, as applicable.

In the case-crossover study, a 90-day hazard window will immediately precede the index event date within which the occurrence of a prescription or dispensing will define exposure status. Similarly, a 90-day referent window will precede the hazard window, with exposure status designated comparably. A 30-day washout window between the hazard and referent windows will be used to mitigate any carryover effects from the prior exposure. Please see **Figure 2** for a visual depiction of the case-crossover study design.

**Figure 2. Case-crossover study design**

### 6.5.2 Outcomes and follow-up

The primary study endpoint is MACE, defined as the composite of:

- Medically attended non-fatal acute myocardial infarction;
- Medically attended non-fatal stroke;
- Cardiovascular-related death.

The secondary endpoints are:

- Individual components of MACE, analyzed separately, as (1) medically attended non-fatal acute myocardial infarction; (2) medically attended non-fatal stroke; and (3) cardiovascular-related death.

In accordance with the CAMELLIA-TIMI 61 trial, the comparability study will examine safety endpoints for the secondary objectives (2.0 and 2.1).

The safety endpoint was defined as a composite of:

- Cardiovascular death;
- Myocardial infarction;
- Stroke.

For all study objectives, information on myocardial infarction and stroke will be obtained from the EHR data, while information on death will be obtained from Datavant. Datavant compiles mortality data from government sources, obituaries, newspapers, and claims data for more than 90% of the U.S. population. Cause of death will be ascertained from the subset of individuals whose records can be linked to death certificates; otherwise, diagnoses adjacent to death will be identified, as feasible, using information from the EHR (e.g., cardiovascular-related hospitalizations or emergency department visits immediately preceding date of death).

A U.S.-licensed physician consultant, blinded to exposure, will review the detailed chronological listing of individual-level EHR data (and claims, where relevant) of a randomly selected subset of apparent MACE cases to determine whether MACE occurred. The adjudication process will compare the operational definition of MACE in the EHR to the physician's professional judgement and the occurrence of MACE in the EHR and claims data. If the initial EHR-based definition of MACE does not meet a pre-specified threshold for concordance, then adjustments to the initial list of diagnoses and procedure codes will be made to improve the accuracy of the operational definition of MACE.

Follow-up time will be calculated separately for each study endpoint. Patients will be followed starting the day after initial exposure until the first of the following censoring events: (1) the study endpoint of interest, (2) death (for those who do not have the endpoint of interest), or (3) end of available data for those who do not have the event of interest (i.e., censoring due to end of available EHR data). Person-time will be calculated by summing the days from cohort entry (day 0) to the date of the first relevant censoring event.

To test the robustness of assumptions about the date of censoring, analyses with differing censoring definitions will be performed, and estimates compared:

- To assess whether the censoring date needs to be adjusted, the physician consultant will review a random sample of patient health profiles to determine whether there is a clear indicator of censoring. Insofar as there appears to be a clear indicator of censoring, the physician will record this date (blinded to exposure), and this information will be used to

adjust the censoring date. Indeed, this information may be treated as an annotation for a machine learning model.

- To account for a patient still being on the insurance plan but not accessing the healthcare system, adjust the end of follow-up to be 6 months, 1 and 2 years following their last healthcare encounter in the EHR.
- To assess the reliability of our method for computing time until censoring in the EHR, compare follow-up times in the EHR to those observed in the claims enrollment files using a subset of those with EHR and claims data.
- To test robustness of the method for computing follow-up time in the EHR, compute the distribution of follow-up times based on enrollment spans within the subset of individuals with claims and EHR data and apply the median follow-up time within populations with particular health profiles.
- To implement a more specific definition of follow-up time, assume that a last healthcare encounter with a primary care provider, endocrinologist, or geriatric care provider in combination with no death information is the end of enrollment.

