### 7.2 Datavant Death Data

We will link data from Arcadia to death data from Datavant, a private U.S. data curator, specializing in organizing health data. Datavant's mortality database contains information on deceased individuals in the U.S. and Canada. Datavant's Death Index contains information on individual deaths including year and month of death, gender, and cause of death, where available. Information is obtained from the Social Security Administration's Death Master File in addition to private obituaries, newspapers and claims data, and is updated on a weekly basis. In 2018, information was present for just over 2.4 million deaths.

In order to de-identify records, names, addresses, and social security numbers are removed in addition to modifications such as changing a person's date of birth to year of birth alone. Datavant's proprietary technology adds encrypted tokens to each record, constructed from the underlying personally identifiable information. Since these tokens correspond to unique individuals, they can be used to link death information to other health-related datasets.

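### Deaths with no ascertainable cause are censored, so some fatal cardiovascular events can leave MACE, and no planned endpoint uses death regardless of cause to show the loss

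*Combined protocol and SAP*

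**What the plan says.** All references are to the combined protocol and SAP.

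- **Endpoint (Section 6.5.2).** MACE and its separately analysed components are "1) medically attended non-fatal acute myocardial infarction; (2) medically attended non-fatal stroke; and (3) cardiovascular-related death". Deaths come from the Datavant source for all study objectives.
- **Cause of death (Section 6.5.2).** There are two routes. The first is "Cause of death will be ascertained from the subset of individuals whose records can be linked to death certificates". For everyone else, "otherwise, diagnoses adjacent to death will be identified, as feasible, using information from the EHR", with "cardiovascular-related hospitalizations or emergency department visits immediately preceding date of death" given as an example. The plan gives no window, code list or expected linked share.
- **Other deaths (Section 6.5.2, follow-up).** Follow-up ends at the endpoint, at "2) death (for those who do not have the endpoint of interest", or at the end of available data. Person-time is summed in days.
- **Death data (Section 7.2).** The index is described as holding "individual deaths including year and month of death, gender, and cause of death, where available".
- **Validation (Section 6.5.2).** A blinded physician reviews a random subset of apparent MACE cases.

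**The concern.** In a cardiovascular safety study, the fatal part of MACE is the part one least wants to lose. A person who dies of an infarction or stroke without reaching care cannot count under the non-fatal components, which must be medically attended. That death enters MACE only if its cause is established. If it is not, the plan ends follow-up as though the death were not an endpoint.

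Three things are at stake: the count of fatal events, the cardiovascular-death contrast if ascertainment of cause differs between arms, and any harm that falls mainly on unattended deaths. The comparison with the 2018 lorcaserin trial and the case-crossover analysis draw on the same death source, so they share the gap.

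**Working it through.** **1. Path of a death.** A certificate-linked cardiovascular death counts, wherever it occurred. Without a certificate, an adjacent EHR cardiovascular diagnosis is needed. With neither, the only rule that applies is censoring at death.

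**2. Would a planned analysis show the loss?**
- Secondary endpoints are the three MACE components. All-cause death is absent.
- Physician review starts from apparent MACE cases. It can find false positives, not missed deaths.
- The listed sensitivity analyses in Section 6.5.2 vary the censoring date, not the handling of deaths of unknown cause.
- Section 10 does not mention missing cause of death.

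**3. Date resolution.** Section 7.2 names year and month. Section 6.5.2 refers to "emergency department visits immediately preceding date of death" and counts person-time in days. In the case-crossover analysis (Section 6.5.1), 90-day windows are anchored on the event date. No rule assigns a day of death.

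**4. The plan's own power figure.** Section 8.2 states more than 80% power for a relative risk of 2.0, at 2 MACE per 1,000 person-years with about 37,000 NB initiators. The text gives no alpha, sidedness or follow-up, and the power figure is not shown, so an exact reproduction is not possible. Assumed here: two-sided alpha 0.05, a mean follow-up of 1 year, and the 16,000 lorcaserin initiators from the abstract.
- Events: 37,000 × 0.004 = 148 and 16,000 × 0.002 = 32.
- SE of the log rate ratio = √(1/148 + 1/32) = 0.195.
- Power = Φ(0.693/0.195 − 1.96), about 94%. With 16,000 per arm, as a rough stand-in for matching weights, it is 89%.
- 80% is reached at a mean follow-up of about 0.63 years (37,000:16,000) or 0.77 years (16,000:16,000).

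The plan's statement is therefore consistent with these assumptions.

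**5. Size of the loss.** Let s be cardiovascular death as a share of true MACE and u the share of those deaths left unclassified. The documents give neither. Assume s = 0.20–0.30 and u = 0.50.
- MACE lost = s × u = 0.10 to 0.15.
- Person-years needed for the same number of events rise by 1/0.90 = 1.11 to 1/0.85 = 1.18.
- With equal loss and a uniform IRR of 2.0, the IRR stays 2.0. The IRD falls from 2.0 to 1.8–1.7 per 1,000 person-years.
- Power at 1 year falls from 94% to 92–91% (37,000:16,000), or from 89% to 86–84% (16,000:16,000).
- Over wider ranges (s = 0.20–0.40, u = 0.25–0.75) the loss is 5–30%, and power at 37,000:16,000 is 93–85%.

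**6. Capture that differs by arm, no true effect.** Take 60% of cardiovascular deaths captured in the NB arm and 50% in the lorcaserin arm.
- Cardiovascular-death IRR = 0.60/0.50 = 1.20.
- MACE IRR at s = 0.20: (0.80 + 0.12)/(0.80 + 0.10) = 1.02.
- MACE IRR at s = 0.30: (0.70 + 0.18)/(0.70 + 0.15) = 1.04.
- Reversing the arms gives 0.50/0.60 = 0.83 for cardiovascular death, and 0.90/0.92 = 0.98 to 0.85/0.88 = 0.97 for MACE.

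**7. Effect not uniform across components (u = 0.50, equal capture).**
- NB doubles all cardiovascular death and nothing else: true MACE IRR 1.20–1.30. Observed (0.80 + 0.20)/(0.80 + 0.10) = 1.11 to (0.70 + 0.30)/(0.70 + 0.15) = 1.18.
- NB doubles only the unclassified deaths: true MACE IRR 1 + s × u = 1.10–1.15, observed 1.00.

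**The case against.** Several stronger readings are tempting, and the documents do not support them.

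- *All out-of-hospital cardiovascular deaths are lost.* No. Certificate-linked deaths at home count, and Section 7.2 lists cause of death in the index where available. The hospital or emergency visit is only an example, so other adjacent EHR diagnoses may qualify.
- *Adjacency cannot be applied because dates are monthly.* Month-only dating is an inference: the list in Section 7.2 is introduced by a word that does not make it exhaustive, and Section 6.5.2 speaks of a date of death. The passages need reconciling. Even a monthly date would allow a coarser rule.
- *Every death is already in hand.* Section 6.5.2 claims sources covering more than 90% of the population, not complete capture.
- *Nothing would look odd.* Cardiovascular death is analysed separately and also enters the composite compared with the 2018 trial, so a discordant result could surface. Neither check would identify missing cause of death as the reason.
- *Capture differs by arm.* No figure shows this. Both arms use the same sources. Claims linkage is about 64% in NB initiators (Section 8.1) and about 46% of EHR patients overall (Section 7.1), but no lorcaserin figure is given, and patient claims linkage is not named as a route to cause of death. The different identification periods (lorcaserin from 2012, NB from September 2014, Section 6.1) make a difference possible, not shown.

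It also stands that equal loss with a uniform effect leaves the IRR unbiased, and that the power statement survives at one year of follow-up. What remains is that deaths with neither source are censored and that no analysis measures how many there are or what they would change.

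**Conclusion.** The point holds in a limited form. As written, the plan can drop cardiovascular deaths of unestablished cause from MACE, and no endpoint counts death regardless of cause. Under the assumed shares this costs 10–15% of MACE events, a modest loss of precision and a smaller IRD. It does not overturn the power claim.

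A reader might infer that the primary IRR is badly distorted. The arithmetic does not support that for unequal capture: the assumed 60% versus 50% moves the null MACE IRR only to about 1.02–1.04. The 1.20 belongs to the cardiovascular-death component. The more serious case for a safety study is an excess concentrated in unclassified deaths, which would read as no effect. How likely that is cannot be judged from the documents. The shares of MACE, the unclassified fraction and the by-arm difference are all assumptions. The correction should be made, since the gap is real and the remedy is cheap.

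**What to change.** 1. Pre-specify two sensitivity endpoints, analysed with the same weighted Poisson model: (a) infarction, stroke or all-cause death; (b) all-cause death alone.
2. Report deaths by arm in three groups: certificate-linked, EHR diagnosis only, and neither.
3. Reconcile Sections 6.5.2 and 7.2 on the resolution of the death date. Then define adjacency, and the assignment of a day of death for person-time and the case-crossover windows, in units that resolution supports.

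Items 1 and 2 matter most. Item 3 alone would only fill in missing detail.

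The cost is a few extra runs and one table on data already being linked. There are three drawbacks. Non-cardiovascular deaths dilute the contrast. Lorcaserin was withdrawn over cancer concerns (Section 5), so all-cause death may differ between arms for reasons unrelated to the heart. A month-level window may label some non-cardiovascular deaths as cardiovascular. For the first two reasons the all-cause endpoints should stay as sensitivity analyses beside the primary MACE definition.
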